**Table 2. List of Primary, Secondary CCI Objectives, Estimands, and Endpoints**

Primary Immunogenicity Objectives	Estimands	Primary Immunogenicity Endpoints
For 20vPnC SC group:		

 
To demonstrate the percentage of participants with predefined serotype-specific IgG concentrations for the 13 serotypes in the 20vPnC SC group are noninferior to the percentage of the corresponding serotypes in the 13vPnC SC group at 1 month after Dose 3
 
	
In participants in compliance with the key protocol criteria (evaluable participants) at 1 month after Dose 3:
 
 
For each of the 13 matched serotypes: difference in the percentage of participants with predefined serotype-specific IgG concentrations between the 20vPnC SC group and the 13vPnC SC group
 
	
 
Pneumococcal serotype-specific IgG concentration
 

 
To demonstrate the percentage of participants with predefined serotype-specific IgG concentrations for the 7 additional serotypes in the 20vPnC SC group are noninferior to the lowest percentage among the 13 serotypes in the 13vPnC SC group at 1 month after Dose 3
 
	
In evaluable participants at 1 month after Dose 3:
 
 
For each of the 7 additional serotypes in 20vPnC: difference in the percentage of participants with predefined serotype-specific IgG concentrations, between the 20vPnC SC group and the lowest percentage of participants with predefined serotype-specific IgG concentrations among the 13 serotypes from the 13vPnC SC group
 
	
 
Pneumococcal serotype-specific IgG concentration
 

For 20vPnC IM group:		

 
To describe the immune responses to 20 serotypes induced by 20vPnC given by IM injection at 1 month after Dose 3
 
	
In evaluable participants at 1 month after Dose 3:
 
 
For each of the serotypes in 20vPnC: difference in the percentage of participants with predefined serotype-specific IgG concentrations between the 20vPnC IM group and the 20vPnC SC group
 
	
 
Pneumococcal serotype-specific IgG concentration
 

**Table 2. List of Primary, Secondary CCI Objectives, Estimands, and Endpoints**

Secondary Immunogenicity Objectives	Estimands	Secondary Immunogenicity Endpoints

 
To demonstrate the serotype-specific IgG GMCs for the 13 serotypes in the 20vPnC SC group are noninferior to the GMCs for the corresponding serotypes in the 13vPnC SC group at 1 month after Dose 3
 
	In evaluable participants at 1 month after Dose 3: 
 
For each of the 13 matched serotypes: GMR of serotype-specific IgG concentrations from the 20vPnC SC group to the 13vPnC SC group
 
	
 
Pneumococcal serotype-specific IgG concentrations
 

 
To demonstrate the serotype-specific IgG GMCs for the 7 additional serotypes in the 20vPnC SC group are noninferior to the lowest IgG GMC among the 13 serotypes induced by the 13vPnC SC group at 1 month after Dose 3
 
	In evaluable participants at 1 month after Dose 3: 
 
For each of the 7 additional serotypes in 20vPnC: GMR of serotype-specific IgG concentration from the 20vPnC SC group to the serotype with the lowest IgG GMC among the 13 serotypes from the 13vPnC SC group
 
	
 
Pneumococcal serotype-specific IgG concentrations
 

 
To further describe the immunogenicity of 20vPnC by both SC and IM injection
 
	In evaluable participants at 1 month after Dose 3: 
 
For each of the serotypes in 20vPnC: GMR of serotype-specific IgG concentrations from the 20vPnC IM group to the 20vPnC SC group
 
	
 
Pneumococcal serotype-specific IgG concentrations
 

	In evaluable participants at 1 month after Dose 4: 
 
For each of the serotypes in 20vPnC: serotype-specific IgG GMCs at 1 month after Dose 4 in each group
 
	
 
Pneumococcal serotype-specific IgG concentrations
 

	In evaluable participants at 1 month after Dose 3 and 1 month after Dose 4: 
 
Serotype-specific OPA GMTs at 1 month after Dose 3, prior to Dose 4, and 1 month after Dose 4 in each group
 
	
 
Pneumococcal serotype-specific OPA titers
 

	In evaluable participants at 1 month after Dose 4: 
 
For each of the serotypes in 20vPnC: percentage of participants with the predefined serotype-specific IgG concentration in each group
 
	
 
Pneumococcal serotype-specific IgG concentrations
 

**Table 2. List of Primary, Secondary CCI Objectives, Estimands, and Endpoints**

Secondary Immunogenicity Objectives	Estimands	Secondary Immunogenicity Endpoints
	In evaluable participants: 
 
GMFRs in serotype-specific IgG concentrations from 1 month after Dose 3 to before Dose 4, from before Dose 4 to 1 month after Dose 4, and from 1 month after Dose 3 to 1 month after Dose 4 in each group
 
	
 
Pneumococcal serotype-specific IgG concentrations
 

CCI		

## 2.2. Study Design

This Phase 3, multicenter, randomized, double-blind, third-party-unblind study will be conducted at investigator sites in Japan. CCI

The purpose of this study is to describe safety and conduct the pivotal immunogenicity comparison of 20vPnC administered by SC injection to the licensed pneumococcal conjugate vaccine, 13vPnC (ie, Prevenar 13®), administered by the currently indicated SC injection in infants CCI. Data will also be generated on 20vPnC administered by IM injection, with the 20vPnC administered by SC injection as a control.

Approximately 666 infants 2 through 6 months of age at the time of consent, by their parent(s)/legal guardian(s), will be enrolled into the study. Participants will be randomized equally to one of the following vaccine groups: (1) 20vPnC SC group, (2) 13vPnC SC group (control vaccine), or (3) 20vPnC IM group. Participants will receive the same vaccine (20vPnC or 13vPnC) by the same injection method (SC or IM injection) for all 4 doses at Visits 1, 2 (4 to 8 weeks after Visit 1), 3 (4 to 8 weeks after Visit 2), and 5 (12 to 15 months of age with  $\geq 60$  days after Dose 3). All vaccine groups will be blinded to all members of the site involved in the study except unblinded site staff who will administer 20vPnC or 13vPnC.

As this study is the first study where 20vPnC is administered subcutaneously and the study participants are infants, a daily enrollment limit of  $\leq 5$  participants will be in place from study start until the study has accumulated safety data from 45 participants through 7 days of follow-up after Dose 1. These data will be carefully monitored and reviewed by the study team. If there are no safety signals in the first 45 participants after Dose 1, the daily enrollment limit will be removed.

Specific vaccines containing Hib, HBV, rotavirus, diphtheria, tetanus, acellular pertussis, and poliovirus antigens will also be administered concomitantly with Doses 1 to 3 (Visit 1, Visit 2, and Visit 3) in the upper arm or orally (in the case of rotavirus vaccine) consistent with the vaccination schedule recommended by the Japan Pediatric Society. Specific vaccines containing Hib, diphtheria, tetanus, acellular pertussis, poliovirus, measles, rubella, and varicella antigens will be administered concomitantly with Dose 4 (Visit 5) in the upper arm(s) consistent with the vaccination schedule recommended by the Japan Pediatric Society. Prompted local reactions (redness, swelling, and pain at the 20vPnC SC and IM or 13vPnC SC injection site), systemic events (fever, decreased appetite, drowsiness/increased sleep, and irritability), and use of antipyretic/pain medications occurring within 7 days after each vaccination will be collected via a provided e-diary (or e-diary application). AEs, including nonserious AEs, will be collected from the signing of informed consent to 1 month after Dose 3 (Visit 4) and from Dose 4 (Visit 5) to 1 month after Dose 4 (Visit 6). SAEs and NDCMCs will be collected for the entire duration of the study.

Blood will be collected 1 month after Dose 3 (Visit 4), immediately prior to Dose 4 (Visit 5), and 1 month after Dose 4 (Visit 6) to assess immunogenicity.

### 3. ENDPOINTS AND BASELINE VARIABLES: DEFINITIONS AND CONVENTIONS

#### 3.1. Primary Endpoints

##### 3.1.1. Primary Safety Endpoints

- Prompted local reactions (redness, swelling, and pain at the injection site) within 7 days after each dose
- Prompted systemic events (fever, decreased appetite, drowsiness/increased sleep, and irritability) within 7 days after each dose
- AEs from Dose 1 to 1 month after Dose 3
- AEs from Dose 4 to 1 month after Dose 4
- SAEs during the study (from Dose 1 to 1 month after Dose 4)
- NDCMCs during the study (from Dose 1 to 1 month after Dose 4)

##### 3.1.1.1. Local Reactions

The local reactions assessed and reported in the e-diary are redness, swelling, and pain at the 20vPnC (SC and IM) or 13vPnC (SC) injection site, from Day 1 through Day 7 after each dose, where Day 1 is the day of each dose. CCI

##### Severity and Maximum Severity

Redness and swelling will be measured and recorded in measuring device (caliper) units, and then categorized during analysis as mild, moderate, or severe based on the grading scale in Table 3. Grade 4 will not be collected in the e-diary but will be collected as an AE on the CRF. Measuring device units can be converted to centimeters according to the following scale: 1 measuring device unit = 0.5 cm. Pain at the vaccine injection site will be assessed by the participant's parent(s)/legal guardian(s) as mild, moderate, or severe according to the grading scale in Table 3.

**Table 3. Grading Scales for Local Reactions**

Local Reaction	GRADE 1 Mild	GRADE 2 Moderate	GRADE 3 a Severe	GRADE 4 b
Redness	1 to 4 caliper units (or measuring device units) = >0 to 2.0 cm	5 to 14 caliper units (or measuring device units) = >2.0 to 7.0 cm	>14 caliper units (or measuring device units) = >7.0 cm	Necrosis or exfoliative dermatitis
Swelling	1 to 4 caliper units (or measuring device units) = >0 to 2.0 cm	5 to 14 caliper units (or measuring device units) = >2.0 to 7.0 cm	>14 caliper units (or measuring device units) = >7.0 cm	Necrosis
Pain at injection site (tenderness)	Hurts if gently touched (eg, whimpers, winces, protests, or withdraws)	Hurts if gently touched with crying	Causes limitation of limb movement	Emergency room visit or hospitalization for severe pain (tenderness) at injection site

Abbreviation: CRF = case report form.

**Note:** If the size of the redness and/or swelling falls between 2 measuring device units, the higher measuring device unit number will be recorded in the e-diary.

- a. Parents/legal guardians of the participants experiencing local reactions >14 caliper units (>7.0 cm) are to be contacted by the study site. An unscheduled visit may be required.
- b. Grade 4 assessment should be made by the investigator. Grade 4 will not be collected in the e-diary but will be collected as an AE on the CRF. The severity of the local reaction should be graded using the AE grading scale.

For each local reaction after each dose, the maximum severity grade will be derived for the e-diary collection period (Day 1 through Day 7, where Day 1 is the day of each dose) as follows:

maximum severity grade = highest grade (maximum severity) within 7 days after vaccination (Day 1 through Day 7) among severity grades reported for that local reaction in the e-diary.

CCI [Redacted]

[Large Redacted Block]

[Redacted]

[Redacted]

CCI

[Redacted]

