#### **8.2.2.1. Local Reactions**

For the first 7 days following each study vaccination (Days 1 through 7, where Day 1 is the day of vaccination), the participant's parent(s)/legal guardian(s) will be asked to assess redness, swelling, and pain at the 20vPnC or 13vPnC injection site (anterolateral thigh) and to record the symptoms in the e-diary in the evening. Redness and swelling will be measured and recorded in measuring device (caliper) units (range: 1 to >14; an entry in the e-diary of 15 will denote >14), and then categorized during analysis as mild, moderate, or severe based on the grading scale in [Table 2](#). Measuring device units can be converted to centimeters according to the following scale: 1 measuring device unit = 0.5 cm. Pain at the vaccine injection site will be assessed by the participant's parent(s)/legal guardian(s) as mild, moderate, or severe according to the grading scale in [Table 2](#). The participant's parent(s)/legal guardian(s) will be prompted to contact the investigator if the participant experiences a severe (Grade 3 or above) local reaction to assess the reaction and perform an unscheduled assessment or visit as appropriate.

Only an investigator is able to classify a participant's local reaction as Grade 4, after physical examination of the participant or documentation from another medically qualified source (eg, emergency room or hospital record). If a participant experiences a Grade 4 local reaction, the investigator must immediately notify the sponsor. Site staff will educate the participant's parent(s)/legal guardian(s) regarding signs and symptoms that would prompt site contact.

The procedure for notification of the sponsor is provided in the ISF or equivalent.

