**Table 2. Grading Scales for Local Reactions**

Local Reaction	Grade 1 (Mild)	Grade 2 (Moderate)	Grade 3 a (Severe)	Grade 4 b
Redness	1 to 4 caliper units (or measuring device units) = >0 to 2.0 cm	5 to 14 caliper units (or measuring device units) = >2.0 to 7.0 cm	>14 caliper units (or measuring device units) = >7 cm	Necrosis or exfoliative dermatitis
Swelling	1 to 4 caliper units (or measuring device units) = >0 to 2.0 cm	5 to 14 caliper units (or measuring device units) = >2.0 to 7.0 cm	>14 caliper units (or measuring device units) = >7 cm	Necrosis
Pain at injection site (tenderness)	Hurts if gently touched (eg, whimpers, winces, protests, or withdraws)	Hurts if gently touched with crying	Causes limitation of limb movement	Emergency room visit or hospitalization for severe pain (tenderness) at injection site

Abbreviation: CRF = case report form.

Note: If the size of the redness and/or swelling falls between 2 measuring device units, the higher measuring device unit number will be recorded in the e-diary.

- a. Parents/legal guardians of the participants experiencing local reactions >14 caliper units (>7.0 cm) are to be contacted by the study site. An unscheduled visit may be required.
- b. Grade 4 assessment should be made by the investigator. Grade 4 will not be collected in the e-diary but will be collected as an AE on the CRF. The severity of the local reaction should be graded using the AE grading scale.

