#### 9.4.2. Safety Analyses

Endpoint	Statistical Analysis Methods
Primary	
 
• Descriptive statistics will be provided for each reactogenicity endpoint for each dose and vaccine group. Local reactions and systemic events from Day 1 through Day 7 after each vaccination will be presented by severity cumulatively across severity levels. Descriptive summary statistics will include counts and percentages of participants with the indicated endpoint and the associated Clopper-Pearson 95% CIs. Between-group differences (20vPnC SC – 13vPnC SC and 20vPnC IM – 20vPnC SC) in percentage and 2-sided 95% CIs will be provided. The Miettinen and Nurminen method will be used to derive the 95% CI for the difference in percentages between vaccine groups.
 
• AEs will be categorized according to Medical Dictionary for Regulatory Activities (MedDRA) terms. A 3-tier approach will be used to summarize AEs. Under this approach AEs are classified into 1 of 3 tiers: (1) Tier 1 events are prespecified events of clinical importance and are identified in a list in the product’s safety review plan; (2) Tier 2 events are those that are not Tier 1 but are considered “relatively common”; a MedDRA preferred term is defined as a Tier 2 event if there are at least 4 of participants in at least 1 vaccine group reporting the event; and (3) Tier 3 events are those that are neither Tier 1 nor Tier 2 events. For both Tier 1 and Tier 2 events, the 95% CIs for the difference in percentage of participants reporting the events between 20vPnC SC and 13vPnC SC groups, or 20vPnC IM and 20vPnC SC groups will be calculated using the Miettinen and Nurminen’s method. In addition, for Tier 1 events, the asymptotic p-values will also be presented for the difference in percentage of participants reporting the events, based on the same test statistic and under the assumption that the test statistic is asymptotically normally distributed. There is no Tier 1 event identified for 20vPnC at this stage. Descriptive summary statistics (counts and percentages and associated Clopper-Pearson 95% CIs) will be provided for Tier 3 events for each vaccine group.
 
• SAEs and NDCMCs will be categorized according to MedDRA terms. Counts, percentages and the associated Clopper-Pearson 95% CIs of SAEs and NDCMCs from Dose 1 to 1 month after Dose 4 will be provided for each vaccine group.
 

Endpoint	Statistical Analysis Methods

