**3.1.1.4. Adverse Events**

AEs will be categorized according to MedDRA terms. AEs will be assessed from the time of informed consent through 1 month after Dose 3 (Visit 4) and from Dose 4 (Visit 5) through 1 month after Dose 4 (Visit 6).

The AE endpoints will be summarized by system organ class and preferred term on a participant level.

This safety endpoint will be supported by summaries and listings of related AEs, severe AEs, and immediate AEs (within the first 30 minutes after each dose).

AE reporting will be based on the specific reporting period. Missing AE start dates will be imputed following the Pfizer data standard rules as described in [Section 5.3](#).

A 3-tier approach will be used to summarize AEs from Dose 1 through 1 month after Dose 3 and, separately, from Dose 4 through 1 month after Dose 4. Under this approach, AEs are classified into 1 of 3 tiers. Different analyses will be performed for different tiers (see [Section 6.1.1.3.1](#)).

- Tier 1 events: These are prespecified events of clinical importance and are identified in a list in the product’s Safety Review Plan. No Tier 1 events have been identified to date for 20vPnC.
- Tier 2 events: These are events that are not Tier 1, but are “common.” A MedDRA preferred term is defined as a Tier 2 event if there are at least 4 participants with the AE term in at least 1 vaccine group.
- Tier 3 events: These are events that are neither Tier 1 nor Tier 2.

[REDACTED]

[REDACTED]

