##### 6.1.1.1.1. Main Analysis

- Estimand: The percentage of participants reporting prompted local reactions (redness, swelling, and pain at the injection site) within 7 days after each dose ([Section 2.1](#)).
- Analysis set: Safety population ([Section 4](#)).
- Analysis time point: Within 7 days after each dose.
- Analysis methodology: The between-group difference (20vPnC SC group – 13vPnC SC group, or 20vPnC IM group – 20vPnC SC group) and the corresponding 2-sided 95% CI will be calculated using the Miettinen and Nurminen method ([Section 5.2.1](#)) for each reaction.
- Intercurrent events and missing data: Missing values will not be imputed. Confirmed e-diary errors will be excluded from the analysis.

- Reporting results: Count and percentage of participants with the indicated endpoint and the associated 2-sided 95% CI for each and any local reaction after each dose in each vaccine group will be presented by maximum severity across severity levels. Between-group differences (20vPnC SC group – 13vPnC SC group, or 20vPnC IM group – 20vPnC SC group) in these percentages and their 2-sided 95% CIs will also be provided. The denominator used in the percentage calculation will be the number of participants with any e-diary data reported after the specified vaccination.

CCI [REDACTED]

[REDACTED]

[REDACTED]

[REDACTED]

[REDACTED]

[REDACTED]

[REDACTED]

[REDACTED]

[REDACTED]

[REDACTED]

[REDACTED]

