### 6.1.1.3. Adverse Events

#### 6.1.1.3.1. Main Analysis

- Estimands:
  - The percentages of participants reporting AEs from Dose 1 to 1 month after Dose 3 (Section 2.1).

- The percentages of participants reporting AEs from Dose 4 to 1 month after Dose 4 (Section 2.1).
- Analysis set: Safety population (Section 4).
- Analysis time points: Dose 1 to 1 month after Dose 3 and Dose 4 to 1 month after Dose 4.
- Analysis methodology: 3-Tiered approach as described in Section 5.2.1.
- Intercurrent events and missing data: No missing values will be imputed except for partial AE start dates (Section 5.3).
- Reporting results: For all 3 tiers, the numerator (n) and the denominator (N) used in the percentage calculation, the percentage (%), and the corresponding 2-sided 95% CI for participants reporting any AE, each system organ class, and each preferred term within system organ class will be presented by vaccine group.
- In addition, for AEs classified as Tier 2 events, the differences in percentages and associated 2-sided 95% CIs (20vPnC SC group – 13vPnC SC group, or 20vPnC IM group – 20vPnC SC group) will be provided.
- Further, for Tier 1 events, if any are identified, the difference in percentages, the associated 2-sided 95% CI for the risk difference, and the asymptotic p-values will also be provided.

CCI [REDACTED]

[REDACTED]

[REDACTED]

[REDACTED]

[REDACTED]

[REDACTED]

[REDACTED]

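### Does the local-reaction severity table hide Grade 4 reactions because it is built from the e-diary alone?

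*SAP*

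**What the plan says.** SAP Table 3, like Protocol Table 2, defines four grades for redness, swelling and pain. For redness and swelling, Grades 1 to 3 are bands of caliper size. Grade 4 is a different kind of finding: necrosis (or exfoliative dermatitis, for redness), or an emergency visit or admission for severe pain. Only an investigator can assign it. It is kept out of the e-diary and recorded on the CRF as an AE, and "The severity of the local reaction should be graded using the AE grading scale".

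SAP 3.1.1.1 then sets the maximum severity for each reaction and dose to the highest grade over Days 1 to 7 "among severity grades reported for that local reaction in the e-diary". SAP 6.1.1.1.1 says that counts and percentages "for each and any local reaction after each dose in each vaccine group will be presented by maximum severity across severity levels". It adds: "The denominator used in the percentage calculation will be the number of participants with any e-diary data reported after the specified vaccination". Protocol 9.4.2 describes the same output, which "will be presented by severity cumulatively across severity levels".

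On the adverse event side, SAP 6.1.1.3.1 gives "Analysis time points: Dose 1 to 1 month after Dose 3 and Dose 4 to 1 month after Dose 4", and SAP 3.1.1.4 promises "summaries and listings of related AEs, severe AEs, and immediate AEs". Protocol 8.2.2.1 adds: "If a participant experiences a Grade 4 local reaction, the investigator must immediately notify the sponsor".

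**The concern.** The plan defines a top grade, reserves it for the investigator, requires immediate notice to the sponsor, and then derives severity from a source that cannot contain it. A reader who sees severe as the highest category cannot tell from that table whether no Grade 4 reaction occurred or none could be shown.

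This deserves a look because describing safety is a primary objective and the trial is the first in which 20vPnC is given subcutaneously, in infants. Protocol 2.3.1 also notes that redness and swelling were somewhat more frequent with subcutaneous than with intramuscular 13vPnC. The adverse event route does not obviously restore the detail: the AE intensity scale ends at severe, the rows are MedDRA terms, and Doses 1 to 3 share one analysis window. If the severity table were the only place to look for the worst local reactions, the safety description could mislead.

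**Working it through.** The plan states no figure on this point, so the check applies the rule to cases and then follows a Grade 4 event through the other outputs.

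**1. What the severity table shows.** One caliper unit is 0.5 cm (SAP 3.1.1.1). The upper limit of Grade 1 is 4 × 0.5 = 2.0 cm, and of Grade 2 it is 14 × 0.5 = 7.0 cm. For assumed participants who each have a Grade 4 event on the CRF:

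| E-diary record after the dose | Tabulated maximum |
|---|---|
| Redness or swelling with necrosis, largest size up to 2.0 cm | Grade 1 |
| Same, above 2.0 and up to 7.0 cm | Grade 2 |
| Same, above 7.0 cm | Grade 3 |
| Emergency visit for pain, parent recorded severe | Grade 3 |
| Diary completed, reaction not entered | No reaction |
| No diary data after that dose | Not in the denominator |

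The rule never returns 4. In the first three rows, however, the recorded size is tabulated correctly. Necrosis is a separate attribute that the diary does not measure, so the table is incomplete about these participants rather than wrong about what it measures.

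**2. Where the same event is reported.**

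- *Main AE analysis* (SAP 6.1.1.3.1): any AE, system organ class and preferred term, by vaccine group, with a confidence interval for every tier. A term reported by fewer than 4 participants in every group is Tier 3 and has no between-group difference, but it still has its count and percentage.
- *Supporting AE outputs* (SAP 3.1.1.4): summaries and listings of severe and of related AEs, where the event meets those descriptions. Listings show individual events, although their columns are not visible.
- *SAE analysis* (SAP 6.1.1.4.1): any event that is serious. Protocol 10.3.2 counts detention in an emergency ward for observation or treatment, tells the investigator to treat doubtful cases as serious, and adds important medical events. Some emergency visits without a ward admission will therefore be SAEs, but not necessarily all.
- *Unscheduled visits* (Protocol 8.11.7): redness or swelling above 7 cm, or severe pain, leads to a telephone contact recorded on the CRF. If a visit takes place, diameters are measured and other findings go to the AE page where appropriate.
- *Sponsor notification* (Protocol 8.2.2.1): immediate, and independent of any table.

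**3. What is not shown.** On the visible text, no output marks an event as Grade 4 or ties it to redness, swelling or pain within Days 1 to 7. The dose is obscured only for Doses 1 to 3, because Dose 4 has its own AE window.

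**4. What rests on the grade.** The estimand in SAP 6.1.1.1.1 is the percentage of participants reporting a prompted local reaction within 7 days of each dose. Grade is a breakdown of that percentage, and no hypothesis, margin or decision rule uses it. The last two rows of the table above are ordinary missing or unreported diary data, which the SAP states it will not impute. They would arise whether or not a Grade 4 category existed.

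**The case for a change.** The best case for a change is that the information cannot easily be rebuilt from the AE tables. Grading on the AE scale replaces the Table 3 label, and severe AE summaries do not separate Grade 4 from other severe events. A preferred term may also mix the Grade 4 case with milder ones. A label on the severity table and a short count by group, dose and reaction would cost little, because the investigator already makes the classification. If the CRF has no field for it, the label could be hard to recover after database lock.

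The facts in this argument stand. They do not make the analysis wrong. Parent-recorded diary grades and investigator diagnoses come from different sources with different denominators. Keeping them in separate outputs is a defensible choice, and the side table proposed would keep them apart too. SAP 3.1.1.1 says openly that redness and swelling are categorized into three levels and that Grade 4 goes to the CRF, so a careful reader is not told that no Grade 4 reaction occurred. The CRF is not among the documents, so whether it lacks a field is unknown. There are also redacted blocks directly after the maximum-severity derivation and directly after the main analysis of local reactions. Either may already provide such a display.

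**Conclusion.** No change to the plan is needed. On the visible text, the local-reaction severity table covers e-diary Grades 1 to 3, and Grade 4 reactions are reported as adverse events on a scale that ends at severe. This is a stated division between two data sources. No event goes unreported, the any-reaction rule is unchanged, and the noninferiority results are unaffected.

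The remaining effect is a missing label, plus pooling over Doses 1 to 3 in the main AE analysis. Its size depends on how many Grade 4 reactions occur, for which the documents give no rate. An analyst would normally deal with it when producing the outputs, by footnoting the table as e-diary Grades 1 to 3 and pointing to the AE listings.

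The conclusion assumes that Grade 4 reactions are entered on the AE page as both documents require, and that the listings promised in SAP 3.1.1.4 are produced. It is limited to local reactions. SAP Table 4 carries the same Grade 4 footnote for systemic symptoms, but no maximum-severity derivation for them is visible, and fever has no Grade 4.
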